1.0 INTRODUCTION

1.1 Background and Scientific Rationale

Irritable bowel syndrome (IBS) is one of the most common gastrointestinal disorders, with a global prevalence of 11% according to a recent meta-analysis ¹. Patients with IBS visit the doctor more frequently, consume more medications, and use more diagnostic tests, such that the total costs of managing IBS in the United States in excess of \$30 billion per year, including indirect costs relating to loss of productivity of more than \$20 billion ². IBS manifests itself in 3 major forms; diarrhea-predominant (IBS-D), constipation-predominant (IBS-C), and mixed (IBS-M) ³, and is predominantly characterized by symptoms of abdominal pain, changes in stool frequency and consistency, and abdominal bloating ⁴. The diagnosis of IBS involves the identification of these key clinical symptoms ^{5, 6}. Abdominal pain/discomfort (i.e. visceral hypersensitivity) is present in all patients and remains the most therapy-resistant symptom in IBS. Apart from abdominal pain, which is measured subjectively using visual scales, several studies have shown a significant increase in rectal sensitivity, which is measured objectively using an inflatable balloon. Hence, drugs which are shown to have objective effects on visceral hypersensitivity are crucial in the management of IBS.

Over the last decade, our group has demonstrated that small intestinal bacterial overgrowth (SIBO) may play a significant role in IBS ⁷⁻¹¹. SIBO is a condition in which there is an increase in the number of bacteria in the small bowel ¹²⁻¹⁴, and typically includes an overgrowth of coliform bacteria which are normally found in the colon ¹⁵. These are predominantly gramnegative aerobes and anaerobic species that produce gas during fermentation of carbohydrates ^{15, 16}, and the SIBO hypothesis proposes that it is this expansion of bacteria in the small bowel that leads to IBS symptoms including bloating, abdominal discomfort and changes in stool form ¹⁷. Two separate studies using cultures of small bowel aspirates have now confirmed that IBS subjects have higher coliform counts in the small bowel than non-IBS subjects ^{15, 18}. Significantly, 60% of IBS-D subjects were found to meet the definition of SIBO ¹⁸.

1.2 Current Standard Therapy

Currently, three drugs for IBS-D (rifaximin, alosetron and eluxadoline) and two (linaclotide and lubiprostone) for IBS-C are approved by FDA ¹⁹. While these drugs have shown to decrease abdominal pain based on subjective scales in their respective clinical trials, there is very little data to substantiate objective changes in visceral hypersensitivity. While rifaximin is an

5

antibiotic, the exact underlying mechanism of action for rifaximin in reducing the pain component of IBS remains unknown. However, rifaximin is the only medication that has been shown in randomized controlled trials to decrease abdominal discomfort in all subtypes of IBS. This suggests that rifaximin, unlike other approved medications, addresses the underlying pathophysiology of IBS rather than simply targeting symptom relief.

Given the role of altered bacterial populations in IBS, a number of randomized controlled trials have been conducted examining the utility of antibiotics in treating IBS ²⁰⁻²³. All of these controlled trials have demonstrated significant success with antibiotic therapy. The two principal antibiotics studied to date are neomycin ⁸ and rifaximin (Xifaxan) ^{21, 24, 25}. While neomycin was a successful therapy for IBS, it was disappointing in its ability to normalize the lactulose breath test (LBT) ⁸. In contrast rifaximin, a non-absorbed antibiotic (99.6% retained in the GI tract), has been shown to normalize the LBT in 70% of subjects ²⁶. The most recent phase III randomized controlled trial of rifaximin demonstrated three important findings ²³:

First, rifaximin was effective in improving the primary endpoint (adequate relief of global IBS symptoms and newer FDA endpoints for IBS) compared to placebo. Second, rifaximin treatment resulted in significantly greater improvement in all major IBS symptoms (abdominal pain, bloating, and stool consistency). Third, the drug had a durable effect for over 3 months after the cessation of therapy²³.

1.3 Rationale for the Study

Currently in clinical practice and research, visceral sensitivity can be objectively, safely, easily and reliably measured using an inflatable rectal balloon attached to a barometer. We hypothesize that rifaximin is effective in decreasing rectal visceral hypersensitivity in IBS patients. In this study, we propose to test this hypothesis. Moreover, we will explore whether this effect is mediated by SIBO and accompanied by improvement in breath test results.

6

2.0 OBJECTIVE

The primary objective of this study is to assess the effect of rifaximin in decreasing rectal hypersensitivity in patients with IBS-M and IBS-D. The secondary objective of this study is to assess the role of SIBO in rectal sensitivity.

3.0 STUDY DESIGN

3.1 Program Type/Scope of Trial/Clinical Design

The proposed study is a prospective clinical trial to determine whether Xifaxan can decrease rectal visceral hypersensitivity in diarrhea-predominant and mixed type IBS patients.

IBS-D and IBS-M patients will undergo baseline rectal sensitivity testing. Patients will then receive rifaximin 550 mg by mouth three times daily for 14 days. On day 15, patients will undergo repeat rectal sensitivity testing.

3.2 Study Population/Demographics/Disorder

Adult patients (age 18-75) with IBS-D or IBS-M (diagnosed based on Rome IV criteria ²⁷) will be assessed for eligibility to participate in this study. Potential subjects will be identified and recruited through the GI Motility Clinic at Cedars-Sinai Medical Center.

3.3 Number of Subjects (Statistical Justification)

We are planning a study of a continuous response variable before and after therapy. In our previous study of 122 patients, we showed that the rectal balloon volume to cause the sensation of urge to defecate had a mean of 87 cc and standard deviation of 42 cc ²⁸. We consider a 20 cc increase in threshold of urge to defecate to be clinically significant. The effect size associated with this assumption is 0.50. We need to study 34 subjects be able to reject the null hypothesis that the rectal sensitivity after rifaximin is equal with probability (power) of 0.8. The Type I error probability associated with this test of this null hypothesis is 0.05. As this is a 4 month follow up study, we expect a 15% dropout rate based on our previous clinical experience. Therefore, we will need to consent 40 subjects to achieve our statistical goals. Statistical analysis will be performed using STATA ver 14.0. Paired t test will be used to assess the primary outcome of interest and selected secondary outcomes. Logistic regression will be used to assess the determinants of responders (improvement of 20 cc in rectal volume to cause urge).

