6.3 Study Flowchart

6.4 Study Duration

The study duration will be approximately 1 year. Each subject will be involved in the study for 3 weeks (see Study Flowchart).

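### The 80% power in section 3.3 is not substantiated: 20/42 is 0.476 rather than 0.50, no SD of the paired change is given, and the dropout rate rests on a follow-up length the schedule contradicts

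*Combined protocol and SAP*

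**What the plan says.** Section 3.3 is the only sample-size justification. It reports that in an earlier study of 122 patients the rectal volume causing an urge to defecate "had a mean of 87 cc and standard deviation of 42 cc", and it takes a 20 cc rise in that threshold as clinically significant. It then states: "The effect size associated with this assumption is 0.50". From this it derives 34 subjects in order to "reject the null hypothesis that the rectal sensitivity after rifaximin is equal with probability (power) of 0.8", and adds: "The Type I error probability associated with this test of this null hypothesis is 0.05". It does not say whether the test is one- or two-sided. On analysis it says: "Paired t test will be used to assess the primary outcome of interest and selected secondary outcomes".

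The step from 34 to 40 consented subjects is explained as follows: "As this is a 4 month follow up study, we expect a 15% dropout rate based on our previous clinical experience".

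The timetable elsewhere is shorter. Section 3.1 says "On day 15, patients will undergo repeat rectal sensitivity testing", section 6.2 runs from day -7 to day 15 with no later visit, and section 6.4 puts each subject's involvement at 3 weeks.

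**The concern.** There are three separate points.

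1. **Effect size.** The two figures just before the stated 0.50 do not give it. An effect size of 0.50 needs an SD of 40 cc or a change of 21 cc, and section 3.3 gives neither.
2. **Wrong kind of SD, or an unstated assumption.** A paired t test depends on the SD of the within-subject change. The 42 cc is described as the spread of the urge volume across patients. The documents give no SD of change, before-after correlation or test-retest figure.
3. **Dropout basis.** A 4-month follow-up is cited for a study in which each subject takes part for 3 weeks.

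The trial is small and compares each patient with his or her own baseline. If the result is null, a reader must be able to tell whether a 20 cc change was reliably detectable. Section 3.3 as written does not allow that.

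**Working it through.** **Inputs (section 3.3):** target change 20 cc; SD 42 cc; stated effect size 0.50; alpha 0.05; power 0.80; 34 completers; 15% dropout; 40 consented. Not given: sidedness, SD of change, before-after correlation.

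**Method:** exact power of the paired t test from the noncentral t distribution, with n − 1 degrees of freedom and noncentrality d·√n, where d = (mean change)/(SD of change).

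**Step 1: reproduce the plan's figure.** With d = 0.50 and a two-sided 0.05 level, n = 33 gives 79.5% and n = 34 gives 80.8%, so 34 is the smallest adequate size. A one-sided test would give 27, so the plan must have used two sides. Dropout: 34/0.85 = 40. Both 34 and 40 therefore follow from 0.50.

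**Step 2: use the plan's own inputs.** d = 20/42 = 0.476. Treating 42 cc as the SD of the change:

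| Completers | Power for 20 cc |
|---|---|
| 34 | 76.9% |
| 36 | 79.3% |
| 37 | 80.5% |
| 38 | 81.6% |
| 40 | 83.6% |

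At 34 completers the shortfall from 80% is 3.1 points. The effect size detectable with 80% power is 0.495, which is 0.495 × 42 = 20.8 cc. The shortfall closes at 37 completers.

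**Step 3: treat 42 cc as the SD of a single measurement.** Assume the same SD before and after treatment, and a correlation ρ between the two. Then SD of change = 42 × √(2(1 − ρ)). This equals 42 only when ρ = 0.5. The stated d = 0.50 implies an SD of change of 20/0.50 = 40 cc, hence ρ = 1 − (40/42)²/2 = 0.55. The values of ρ below are assumptions chosen to show the range.

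| ρ | SD of change (cc) | Power at 34 | Completers for 80% |
|---|---|---|---|
| 0.3 | 49.7 | 62% | 51 |
| 0.4 | 46.0 | 69% | 44 |
| 0.5 | 42.0 | 77% | 37 |
| 0.6 | 37.6 | 85% | 30 |
| 0.7 | 32.5 | 94% | 23 |

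Break-even for 80% power at 20 cc:

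| Completers | Largest SD of change (cc) | Smallest ρ |
|---|---|---|
| 34 | 40.4 | 0.54 |
| 38 | 42.9 | 0.48 |
| 40 | 44.0 | 0.45 |

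**Step 4: dropout.** Section 3.3 says 4 months; sections 3.1, 6.2 and 6.4 give a retest on day 15 and 3 weeks in total. Power at 34 completers is unaffected. If fewer than 15% drop out over 3 weeks, there are more completers and power rises.

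**The case against.** The strongest reply is that 0.476 is 0.5 to one decimal, so the first point is rounding. It costs about 3 points of power, or 0.8 cc in detectable change, and the 37 completers needed fit within the 40 to be consented. That is fair as to size, and it is the smallest of the three points. But the value is printed to two decimals, where the correct figure is 0.48, and it was carried into the sample size.

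A second objection is that the first two points pull against each other: if 42 cc is not the SD of the change, then 20/42 is not the effect size of the planned test either. This is why the 76.9% is stated only conditionally. On either reading 0.50 is unsupported: it does not follow from 42 cc, and the SD of change of 40 cc that it would need is not given.

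Third, no underpowering has been shown. That stands. The correlations are assumed, and at 0.6 or 0.7 the plan has more than 80% power.

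Fourth, the 4-month phrase looks like leftover text: the budget in section 11.0 allows 80 compensated visits, or two for each of 40 subjects. The dropout sentence also cites clinical experience. Both remarks are fair, and the point does not weaken power. The contradiction still has to be removed, because the stated reason for 15% does not describe this study.

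**Conclusion.** The concern holds. The effect size of 0.50 is wrong as written, since 20/42 = 0.476. If the SD of the paired change is 42 cc and the test is two-sided at 0.05, 34 completers give 76.9% power for 20 cc, and 80% requires 37. The more consequential defect is that the SD of change is not stated: with equal SDs before and after, assumed correlations of 0.3 to 0.7 put power at 34 anywhere from 62% to 94%. The trial is not shown to be underpowered; its claim of 80% power is unsupported in either direction. The conflict between 4 months and 3 weeks is a separate inconsistency that leaves the 15% dropout without a valid stated basis and does not reduce power. This should be fixed.

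**What to change.** Revise section 3.3 as follows.

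- Restate the calculation: effect size 20/42 = 0.48; with 34 completers, 77% power for 20 cc (80% for 20.8 cc) at two-sided 0.05, if the SD of the paired change is 42 cc.
- State the assumed SD of the change and where it comes from, and show power across before-after correlations of 0.3 to 0.7.
- Say that the test is two-sided, which 34 already implies.
- Reconcile the 4-month and 3-week statements, and base the dropout rate on the actual 3-week participation.

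The cost is wording in one section; this restatement leaves enrolment, test and endpoint as they are. The downside is a slightly less favourable stated power. If the SD of change, once stated, exceeds about 44 cc, 80% power for 20 cc is out of reach even if all 40 complete, and the section should then report the power it does have.

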7.2 Secondary Outcome Measures

Secondary outcome measures will include:

- mean change in the balloon pressure and volume that leads to first urge to defecate
- mean change in the balloon pressure and volume that leads to severe urge to defecate
- mean change in the balloon pressure and volume that leads to severe urge to defecate
- mean change in the balloon pressure and volume that leads to severe urge to defecate
- mean change in the balloon pressure and volume that leads to first sensation
- mean change in the balloon pressure and volume that leads to first sensation
- mean change in the balloon pressure and volume that leads to first sensation
- Association of urgency symptom and rectal sensitivity testing
- Normalization of LBT as a predictor of improvement of rectal hypersensitivity

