Appendix 2: Lactulose Breath Test

Preparation for the Test:

Subjects will not be allowed to consume any heavy protein or legumes on the night before the test.

Subjects will fast beginning at 7 pm on the previous evening to guarantee a 12 hour fast. Only water will be allowed until midnight before the test. Subjects cannot chew gum during this time of fasting.

All subjects will be asked to brush their teeth or use mouthwash (not swallowed) and refrain from smoking cigarettes on the morning of the test.

Test Administration:

All subjects will provide a baseline end expiratory breath sample at the start of the test.

They will then be provided a syrup containing 10 g of lactulose syrup after which breath samples will be collected every 15 minutes exactly for 120 minutes.

Sample Analysis:

Samples will be analyzed using a gas chromatograph capable of measuring hydrogen (H₂), methane (CH₄) and carbon dioxide (CO₂). The CO₂ will be used to correct for alveolar sampling error. The H₂ and CH₄ will be plotted on a graph with time on the x-axis and gas concentration in ppm on the y-axis.

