Appendix 5: Assessment of rectal sensitivity using graded balloon distention

A standard non-latex rectal balloon (Mui Scientific, Mississauga, Ontario, Canada) will used for assessment of rectal sensitivity. After lubrication the balloon will be inserted into the rectum and will be advanced for 5 cm. The balloon will be inflated by 20 cc and pull back until sphincter resistance is appreciated. At this point the catheter will be advance 3cm and will be deflated. Following a 20 second hiatal, every minute the balloon will be inflated by 10 cc in 10 seconds. Patient will be asked about the sensation after 10 seconds. Patients will be blinded from the balloon volume or whether the balloon is inflated. The balloon will be deflated and inflated with 10cc incremental volumes until the first sensation, first sensation of urge, normal sensation of urge and severe sensation of urge is appreciated (see scale below). When these points are achieved, the balloon pressure will also be recorded (Posey 8199 Manometer, Arcadia, CA, USA). The maximum inflated volume will be 200 cc.

0- No sensation: No fullness is sensed in the rectum

20- First sensation: Feeling fullness in the rectum but no urge (would not go or plan to go to restroom)

40- First sense of urge to defecate: Sensation of fullness and mild urge to defecate (would not go to bathroom)

60- Normal urge to defecate: Usual sensation of urge to defecate (would plan to go restroom but would not rush)

80- Severe urge to defecate: Would stop any non-essential activity and rush to a bathroom.

100- Pain: Sensation of pain/discomfort different from urge.

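### Section 3.3 names only a logistic regression on a 20 cc cut to assess determinants; a linear model of Day 15 urge volume adjusted for baseline should be the main test, with the responder model kept beside it

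*Combined protocol and SAP*

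**What the plan says.** Section 3.3 describes the outcome as continuous: "We are planning a study of a continuous response variable before and after therapy". It plans from a mean of 87 cc and an SD of 42 cc, and assigns a paired t test to the primary outcome and to some secondary ones. It also sets the size of change that matters: "We consider a 20 cc increase in threshold of urge to defecate to be clinically significant".

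For determinants it names one method: "Logistic regression will be used to assess the determinants of responders (improvement of 20 cc in rectal volume to cause urge". It lists no covariates. It neither mentions nor rules out baseline volume as one, and it names no linear model.

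Sections 3.1 and 6.2 schedule rectal sensitivity testing before treatment and on Day 15. Appendix 5 fixes the resolution of the measurement: "The balloon will be deflated and inflated with 10cc incremental volumes until the first sensation", up to a maximum of 200 cc.

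**The concern.** The cut is two inflation steps wide. A subject who gains 10 cc and one who gains 20 cc fall in opposite classes, while gains of 20 cc and 100 cc count the same. If the mean change is near the 20 cc that the plan hopes for, the cut lies at the centre of the distribution, where a one-step difference most often changes a subject's class.

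The plan expects about 34 completers, so any determinant analysis is short of power already. Section 1.3 raises a question of this kind: "we will explore whether this effect is mediated by SIBO and accompanied by improvement in breath test results". If the only prespecified model discards much of the measured change and leaves out baseline volume, a characteristic that does shift urge volume is more likely to be missed.

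**Working it through.** **The plan's own figure.** A paired t test with effect size 0.50, two-sided alpha 0.05 and power 0.80 needs n = 34 (power 0.808). The plan does not state sidedness, but two-sided reproduces its number. Then 34/(1 − 0.15) = 40. Both stated numbers are recovered, and nothing below changes them.

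**Inputs from the documents.** Mean 87 cc, SD 42 cc, cut 20 cc, 34 completers (Section 3.3); 10 cc steps and 200 cc ceiling (Appendix 5).

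**Assumed.** The documents give no SD of change and no pre-post correlation ρ. The stated effect size ("The effect size associated with this assumption is 0.50") corresponds to an SD of change of 20/0.50 = 40 cc. With 42 cc at each visit this means ρ = 1 − 40²/(2 × 42²) = 0.546. Other values of ρ are shown as a range.

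**Information kept by the cut.** For a normal change with mean m and SD s, and a small uniform shift, the relative efficiency is φ(z)²/[p(1 − p)], where z = (20 − m)/s and p is the proportion above the cut.

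- m = 20, any s: z = 0, so 0.3989²/0.25 = 0.637.
- m = 0 or 40, s = 40: z = ±0.5, so 0.3521²/(0.3085 × 0.6915) = 0.581.
- m = 0 or 40, s = 50 (ρ = 0.3): 0.601. With s = 27 (ρ = 0.8): 0.520.

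At s = 40 the cut keeps 58-64%. Since 34 × 0.637 ≈ 21.7 and 34 × 0.581 ≈ 19.8, this is like losing about 12 to 14 of 34 subjects.

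**Simulated power, normal change.** Baseline mean 87, SD 42 at each visit, volumes rounded up to 10 cc steps, cap 200 cc, overall mean change 20 cc, response = change of at least 20 cc. Tests are two-sided at 5%, with likelihood ratio tests for the logistic models; 20,000 runs (10,000 for logistic with baseline).

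| Groups, ρ | Difference | Logistic | Logistic + baseline | Continuous change | Linear + baseline |
|---|---|---|---|---|---|
| 17 v 17, 0.546 | 0 cc | 5.9% | 6.1% | 4.9% | 4.8% |
| 17 v 17, 0.546 | 20 cc | 22% | 25% | 29% | 35% |
| 17 v 17, 0.546 | 30 cc | 43% | 47% | 56% | 65% |
| 14 v 6, 0.5 | 0 cc | 7.1% | 7.9% | 4.7% | 5.2% |
| 14 v 6, 0.5 | 20 cc | 14% | 18% | 15% | 18% |
| 14 v 6, 0.5 | 30 cc | 24% | 28% | 28% | 34% |

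At 17 v 17 and 30 cc, plain logistic against linear with baseline is 31% v 55% for ρ = 0.3 and 73% v 90% for ρ = 0.8.

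The 14 v 6 split is only a scenario. It takes 60% with overgrowth (Section 1.1) of 34, about 20, and 70% normalization (Section 1.2) of those, which is 14.

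**Separating cut from covariate.** At 17 v 17 and 30 cc the cut costs 56 − 43 = 13 points with baseline in neither model, and 65 − 47 = 18 with baseline in both. Adding baseline to the continuous analysis gains 65 − 56 = 9. Baseline helps because, with equal SDs, change correlates with it at −√[(1 − ρ)/2], which is −0.50 at ρ = 0.5.

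**Other shapes of response (17 v 17).**

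- Double-exponential error, 30 cc, ρ = 0.5: logistic 50%, continuous change 55%, linear with baseline 67%. The cut costs about 5 points and the covariate adds about 12.
- The same at ρ = 0.8: 89%, 88%, 90%. The cost is gone.
- All-or-none response (a 40 cc gain or none; 70% v 30% gaining): with visit noise of 10 cc, logistic 50% v linear with baseline 47%; with noise of 20 cc, 24% v 28%.

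**The case against.** The best defence is that the responder model answers a legitimate question. The plan calls 20 cc clinically significant and asks who reaches it. A linear model asks what shifts mean volume, which is a different question. This stands, and it is why the logistic model should be kept.

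A reader might infer that the cut always throws away a third or more of the information. The documents do not support that: they give no distribution of change, and the figure needs normality and a uniform shift. With heavy tails or an all-or-none response, the cost is small, absent or slightly reversed. Part of the 43%-to-65% gap is the baseline covariate, which Section 3.3 does not forbid in the logistic model. The 30 cc difference is also 1.5 times the plan's own clinically significant change. At 14 v 6 and 20 cc, with baseline in both models, power is 18% either way, although the logistic tests reject 7-8% under the null there, which flatters them slightly.

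A reader might also infer that the breath-test question is committed to this model. Section 7.2 lists "Normalization of LBT as a predictor of improvement of rectal hypersensitivity" but assigns it no method, so that cannot be said. Nor does Appendix 2, which says the gases "will be plotted on a graph with time on the x-axis and gas concentration in ppm on the y-axis" and gives no criterion for normalization, show any bias. The missing criterion, the missing rule for a normal baseline breath test and the missing Section 7.2 method are gaps in detail and form no part of this point.

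What remains is that the linear model uses data already collected, held its type I error near 5%, and did as well or better in nearly every setting tried. The exception was a 3-point deficit in the low-noise all-or-none case.

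**Conclusion.** The point holds as an inexpensive improvement to an exploratory analysis. It does not show that the planned test is invalid. Section 3.3 names only a dichotomized model for determinants, where a baseline-adjusted linear model on the same measurements would usually be the better main test.

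Under a normal change with a uniform shift and an assumed SD of change of 40 cc, the cut keeps 58-64% of the information. At 17 v 17 and 30 cc it costs 13 to 18 points of power. That size depends on the assumed correlation, group split and shape of response. Where the cut itself costs little, most of any remaining gain comes from the baseline covariate. Neither model makes small, unbalanced comparisons informative.

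The primary outcome is already analysed as continuous, so the paired t test and the numbers 34 and 40 are unaffected.

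**What to change.** In Section 3.3, add a linear regression of Day 15 urge volume on the determinant with baseline urge volume as covariate, and prespecify it as the main test of determinants. Keep the 20 cc responder logistic regression beside it, also with baseline volume as covariate, to answer who reaches the clinically significant change. Label both exploratory.

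The cost is a sentence or two and no new data. The downsides are that the main result is in cc and not an odds ratio, that it does not itself say who reaches 20 cc, and that a linear model is more sensitive to outliers with 34 subjects. With a single arm, both models describe associations with change, not with a treatment effect.
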